## ECG

All-important abnormalities from the ECG readings will be reported.

The percentage of participants with increases in QTc of <30, 30-60, or > 60 ms from baseline will also be tabulated at each time point.

Abnormality Code	ECG parameter			
	HR	PR	QRS	QT Corrected
Abnormalities on actual va	alues			
"Abnormally low"	≤ 50 bpm	NAP	≤ 50 ms	-
"Abnormally high"	≥ 120 bpm	≥ 210 ms	≥ 120 ms	-
["[450 ms, 480 ms]	-	-	-	450 ms < QTc ≤ 480 ms
["[480 ms, 500 ms]	-	-	-	480 ms < QTc ≤ 500 ms
"More than 500 ms	-	-	-	QTc > 500 ms
Abnormalities on changes from baseline				
"[30; 60] ms"	-	-	-	[30; 60] ms
"> 60 ms"	-	-	-	> 60 ms

## **Appendix 5: Paternity Questionnaire**

## **Paternity Questionnaire**

Please answer the following questions:

Did you father a child(ren) after your start of the trial?

Yes 🗆	No 🗆
-------	------

If yes, how many? \_\_\_\_\_

- What month and year was/were your child(ren) born? (Add more lines if necessary)
  - Child 1: MMM/YYYY
  - Child 2: MMM/YYYY
  - Child 3: MMM/YYYY

1.0 / 15 Feb 2021	Initial version	
1.1 / 20 Dec 2022	Updates made to outcome analysis and circulated for comment	
1.2 / 30 Jan 2023	Updates made to Statistical analysis and circulated for further comments	
1.3/ 06 Feb 2023	Updates made to outcome sections to align more with the protocol Additional analysis details added	
1.4/ 02 Mar 2023	Updates made post expert review	
1.5/ 14 Mar 2023	Further updates made after expert review	
1.6/ 17 April 2023	Updates made to section on pharmacokinetics	

1. Introduction

This document outlines the statistical analysis for the BPaMZ/SEM trial, Protocol Version 4.0, dated 07 April 2022.

Pretomanid is being used in an antimicrobial combination regimen(s) to treat patients with pulmonary tuberculosis. The primary purpose of this trial "BPaMZ/SEM" is to evaluate the potential effect of pretomanid on human testicular function whilst being used in a 26-week antimicrobial combination regimen consisting of bedaquiline (B) plus pretomanid (Pa) plus moxifloxacin (M) and pyrazinamide (Z) (BPaMZ).

All participants will receive the same regimen of BPaMZ once daily for 26 weeks.

The participant population will be patients with drug resistant TB (DR-TB) defined as Mycobacterium tuberculosis (MTB) that is sensitive to fluoroquinolones but

- 1. Mono-resistant to rifampicin or isoniazid, OR
- 2. Resistant to both rifampicin and isoniazid (MDR-TB)

2. Objectives

The primary objective is to assess the male reproductive safety of pretomanid in the regimen (BPaMZ) of bedaquiline 200mg (200mg daily for 8 weeks then 100 mg daily for 18 weeks), together with pretomanid 200 mg (1x daily) + moxifloxacin 400 mg (1x daily) + pyrazinamide 1500 mg (1 x daily) for 26 weeks in participants with Drug-resistant (DR) pulmonary TB.

The secondary objective is to evaluate the efficacy, safety and tolerability after 26 weeks of active treatment for TB and follow up for 52 weeks after start of the above described treatment regimen in participants with Drug-resistant (DR) pulmonary TB.

3. Sample Size

A total of 20 evaluable male participants diagnosed with DR-TB who completed the trial will be required.

Twenty-five participants (25) will be enrolled in the trial assuming a 20% participant dropout of the trial. If the dropout rate is higher than 20% before finishing 26 weeks of treatment, the enrolment of additional participants may be considered to assure that 20 complete.

The sample size is not based on formal statistical considerations. It is based on practicality of enrolment and to rule out any severe effect of the regimen on sperm production.

4. Primary Outcome

The primary outcome (endpoint) will be change from baseline in total sperm count at 26 weeks of therapy.

5. Secondary male reproductive toxicity outcomes

1. Change from baseline in all semen parameters (semen count and semen concentration) at 13,

26 and 44 weeks.

- 2. The proportion of subjects experiencing an increase or decrease in sperm count and sperm concentration from baseline to the timepoint of interest (26 weeks and 44 weeks) will be calculated.
- 3. The proportion of subjects experiencing at least a 50 percent increase or decrease in sperm count and sperm concentration from baseline to the timepoint of interest (26 weeks and 44 weeks) will be calculated.
- 4. Change from baseline (at screening) in male reproductive hormones at Week 2, 4, 8, 12, 16, 26, 35, 44, 52, 65, 78 and at early withdrawal. Reproductive hormones: luteinizing hormone (LH), follicle-stimulating hormone (FSH), Inhibin B, testosterone, and total testosterone
- 5. Plasma concentration of pretomanid from sparse sampling will be summarised as descriptive statistics.

6. Other secondary outcomes

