### Objective of the trial:

This study is intended to rule out clinically significant severe adverse effects on testicular function.

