# All semen samples must be separated by no less than 48 hours and preceded by no less than 48 hours of sexual abstinence.

At week 12-13, week 26-27, and week 44-45 timepoint two (XX) semen samples must be collected within those weeks. These two (XX) samples will be averaged to make up the week 12, week 26 and week 44 semen sample values.

For week 12-13, week 26-27 and week 44-45 timepoints, a 14-day collection window is allowed with the aim of the (XX) semen samples to have about a 7-day separation between samples for these timepoints.

Early withdrawal: After 18 weeks of treatment at any early withdrawal thereafter, two (XX) semen samples must be collected. These two samples per timepoint will also be averaged to make up the early withdrawal week semen sample value.

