# **Trial Design Rationale**

The primary purpose of this Male Reproductive Safety – "BPaMZ/SEM"- clinical study is to generate data to evaluate the potential effect of once daily 200mg Pretomanid on human testicular function whilst being dosed for 6 months in patients with Drug Resistant (DR-TB) Pulmonary Tuberculosis. The 6 months dosing period covers current use of pretomanid is an approved antimicrobial regimen for the treatment of TB. (Pretomanid in combination regimen with Bedaquiline and Linezolid (BPaL) for people with XDR-TB or treatment-intolerant/non-responsive MDR-TB). It is not feasible to evaluate the potential testicular toxicity of once daily 200mg Pretomanid in this BPaL regime, as Linezolid has shown toxicity on testicular function in non-clinical studies. Therefore, the study will be conducted using the antimicrobial regimen consisting of Bedaguiline (B) plus Pretomanid (Pa) plus Moxifloxacin (M) and Pyrazinamide (Z) (BPaMZ) for 6 months in DR-TB patients. Participants will also be followed up to 18 weeks post dose to evaluate and ensure coverage of potential recovery of semen parameters which encompasses one and one-half cycles (cycle length is around 75 days) of the seminiferous epithelium. This also includes epididymal transit time (since we are sampling and evaluating semen), which adds another  $\sim 10$  days. Thus, in days 75 + 37.5 + 10 = 122.5 days or 17.5 weeks, therefore 18 weeks should be sufficient for follow-up period.

The safety of pretomanid has been tested in 10 single- and multi-dose Phase I studies with healthy adult male and female participants, receiving single oral doses of pretomanid ranging from 50 to 1500 mg and multiple oral doses ranging from 200 to 1000 mg/day given for up to eight days. Pretomanid has also been studied in combination regimens in patients for up to 9 months in Phase 2 and 3 studies. For this study adult male DR-TB patients who can complete the trial will be required.

For assessment of the male reproductive safety profile the following parameters will be evaluated in adult male participants with Drug Resistant (DR-TB) Pulmonary Tuberculosis.

For assessment of the male reproductive safety profile the following parameters will be evaluated.

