## 9.4 Safety Monitoring

#### **Medical Monitoring:**

During the conduct of the study, it is the responsibility of the sponsor-appointed medical monitor of the study to consult with the investigator(s) and fertility experts regarding any medical concerns or questions that arise. When requested by an investigator, the Medical Monitor discusses and reviews potential participants and helps the investigator ensure that only participants who are appropriate and who meet the protocol inclusion and exclusion criteria are enrolled in the study. The Medical Monitor also ensures that the protocol-specified procedures are followed, especially safety and tolerability data, and that there are no potential safety concerns. The Medical Monitor will review all SAE's regarding this study and any Severe AEs and clinically significant safety concerns.

Regarding the reproductive safety of this study, a reproductive safety monitoring committee will be formed consisting of three fertility experts – these fertility experts should have previously served on a reproductive safety monitoring committee – and the medical monitor. This reproductive safety monitoring committee will convene after the first 4 patients enrolled and then quarterly thereafter to review the reproductive parameters.

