7.6. General Statistical Considerations for Analysis

There are three planned analyses that will be performed. The first analysis will be done after all participants have completed the 26 weeks of treatment. The analysis will be on primary outcome data (semen data), secondary reproductive data, culture conversion data up to week 26 and safety data. The second analysis will be done at week 44 and will also be on the semen data available at 44 weeks, secondary reproductive data, culture conversion data to week 44 and safety data. The final analysis will take place after 78 weeks and will include analyses on all data including the TB efficacy analysis as outlined in §6.1.

There will be no specific strategy to deal with missing data i.e. it will not be imputed. A complete case analysis will be performed.

For the safety analysis, if there are multiple assessments in a visit, the highest grade non-missing value within a visit will be used in the summaries, however all will be shown in the listings. If numeric

data is beyond range of lab detectability and result is showed as "<XX" or ">XX" then the numeric XX value will be used for summary statistics.

Baseline is defined as last available measurement prior to dosing and post baseline abnormalities are included in the summary if the subject did not meet the abnormality criteria at baseline or toxicity grade at post baseline is higher than that on baseline.

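### The 50% sperm-fall outcome leaves out Week 13 and early-withdrawal samples, so a man with such a fall and no Week 26 or 44 sample is not counted in it

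*SAP*

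**What the plan says.** SAP section 5 lists the semen outcomes. Item 1 is "Change from baseline in all semen parameters (semen count and semen concentration) at 13", 26 and 44 weeks. Item 2 is "The proportion of subjects experiencing an increase or decrease in sperm count and sperm concentration from baseline to the timepoint of interest", with Weeks 26 and 44 named. Item 3 adds a size threshold, counting men who reach or exceed "a 50 percent increase or decrease in sperm count and sperm concentration from baseline to the timepoint of interest (26 weeks and 44 weeks". Week 13 appears in item 1 only.

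On missing data, SAP 7.6 says that "it will not be imputed. A complete case analysis will be performed". SAP 8.1.1 uses whatever data exist at each timepoint and gives no carry-forward or worst-value rule.

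The protocol (1.1.1 footnote f, and 8.2.1) collects a pair of semen samples at Weeks 12-13, 26-27 and 44-45. On early withdrawal it says: "After 18 weeks of treatment at any early withdrawal thereafter, two (XX) semen samples must be collected". Protocol 6.3.1 also asks for a semen pair at early withdrawal, during treatment or follow-up, but states no 18-week limit. SAP section 5 names early withdrawal as a timepoint for hormones (item 4) but not for semen.

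The synopsis gives the aim: "This study is intended to rule out clinically significant severe adverse effects on testicular function".

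**The concern.** Item 3 is the only semen outcome in the plan with a threshold for the size of a fall, so it is the most direct answer to the stated aim. As written, it describes men who still give semen at Week 26 or Week 44. The aim concerns treated men. The two groups differ if men who show a fall are more likely to leave.

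The documents leave room for that. A reproductive safety committee is to "convene after the first 4 patients enrolled and then quarterly thereafter to review the reproductive parameters" (protocol 9.4), and the investigator may withdraw a man for safety (protocol, Discontinuation from Treatment/Trial). SAP section 3 also allows extra enrolment, if dropout exceeds 20%, so that 20 men complete. That would add stayers to the count without restoring the men who left.

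**Working it through.** **Inputs.** 20 evaluable men, 20% dropout and 25 enrolled (SAP section 3). A spermatogenic cycle of about 75 days and epididymal transit of about 10 days (protocol 2.1, Trial Design Rationale, in the sum "75 + 37.5 + 10 = 122.5 days"). The number k of leavers with a fall of at least 50% at Week 13 is not given anywhere, so it is run over its full range.

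**1. The plan's own figure.** 20 / (1 − 0.20) = 25, which matches. The planned loss is 25 − 20 = 5 men.

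**2. Where a Week 13 fall goes when no Week 26 or 44 sample follows.**

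| Planned output | Does it include his Week 13 value? |
|---|---|
| Item 1, change from baseline at Week 13 (mean, SD, median, IQR, range) | Yes, but it does not count falls of 50% |
| Shift table at Week 13 (SAP 9.2) | Only if he was within the reference range at baseline and moved out of it |
| Item 3, at least 50% change | No: in neither numerator nor denominator |
| PK summary by 50% change (SAP 9.3, item 2) | Unclear: no timepoint is named |

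The shift table does not replace the 50% count. It misses a man who halves but stays in range, and a man who starts below range. An early-withdrawal semen pair is assigned to no semen outcome. The SAP 7.5 rule on slotting unscheduled visits could at most bring in a pair taken close to Week 26.

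**3. Why Week 13 is informative.** One cycle plus transit is 75 + 10 = 85 days, and 85 / 7 = 12.1 weeks. The Week 12-13 pair is therefore about the first that can show a full-cycle effect.

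**4. Hypothetical range.** Assume 25 men dosed, 5 lost before Week 26 with no later semen, no replacements, no 50% fall among the 20 stayers, and a Week 13 pair from all 5 leavers. Intervals are exact (Clopper-Pearson) 95%: lower limit = 2.5% quantile of Beta(x, n − x + 1), upper limit = 97.5% quantile of Beta(x + 1, n − x). For x = 0 the lower limit is 0 and the upper limit is 1 − 0.025^(1/n), which is 16.8% for n = 20 and 13.7% for n = 25.

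| k | Week 26 count as planned | Fall at any on-treatment sample |
|---|---|---|
| 0 | 0/20 (0 to 16.8%) | 0/25 = 0% (0 to 13.7%) |
| 1 | 0/20 (0 to 16.8%) | 1/25 = 4% (0.1 to 20.4%) |
| 2 | 0/20 (0 to 16.8%) | 2/25 = 8% (1.0 to 26.0%) |
| 3 | 0/20 (0 to 16.8%) | 3/25 = 12% (2.5 to 31.2%) |
| 4 | 0/20 (0 to 16.8%) | 4/25 = 16% (4.5 to 36.1%) |
| 5 | 0/20 (0 to 16.8%) | 5/25 = 20% (6.8 to 40.7%) |

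The planned figure is the same whatever k is. The denominator shrinks if some leavers go before Week 13: with k = 3 and the other two gone by then, it is 3/23 = 13% (2.8 to 33.6%).

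**The case against.** A reader might infer that a Week 13 collapse would go unseen. The documents do not support that. The value enters the Week 13 change summary, where an extreme absolute fall would set the end of the range. It may enter the shift table. Hormones are summarised at Weeks 12 and 16 and at early withdrawal, adverse events leading to withdrawal are tabulated, listings are planned, and the committee reviews reproductive data quarterly. With about 25 men, such a case would probably be noticed. What stands is that no planned table clearly counts it as a 50% fall.

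A reader might also infer that a man who leaves between Weeks 13 and 18 has no early-withdrawal semen. That follows from footnote f and section 8.2.1 but is contradicted by section 6.3.1. The visit description in protocol 1.1.1 adds to the doubt, because it limits the early-withdrawal visit to SAE and TB outcome information and lets it be telephonic. Whether a pair exists is unsettled. If one does, item 3 still does not use it.

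Outcome-related dropout is not shown. No text makes a sperm fall a withdrawal criterion, the safety example given for withdrawal is TB-related, and the reproductive stopping rules were still to be written (protocol 9.4). Protocol 6.4 also recognises men who stop treatment but complete follow-up, so stopping need not mean missing Weeks 26 and 44. This stands, and it is why the table above is a range that includes k = 0. The planned interval of 0 to 16.8% also already covers the point estimates up to k = 4.

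Two smaller points also stand. Week 26 is the primary timepoint and Week 44 the recovery one, and Week 13 only just reaches 85 days: if the seven-day visit window applies, a sample could fall on day 84 − 7 = 77. Item 2 has no size threshold, so the argument about severe falls does not extend to it.

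**Conclusion.** The point holds for item 3. Limiting the 50% outcome to Weeks 26 and 44 under a complete-case rule leaves out any man whose qualifying fall is seen only at Week 13 or at an early-withdrawal visit and who has no later scheduled sample. The omission is certain from the text. A bias is not: it needs leaving to be related to the fall, and then it runs towards reassurance.

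On the planned dropout, up to 5 of 25 men could be affected. With no falls among the stayers, the reported 0/20 is compatible with an on-treatment figure anywhere from 0% to 20%. That span rests on the assumptions in step 4 and does not estimate what will happen. The primary outcome, change in total sperm count at Week 26, is defined as before. This is a cheap improvement.

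**What to change.** 1. In SAP section 5, item 3, change the timepoints to 13, 26 and 44 weeks. Item 2 may be aligned for consistency.
2. Add one supportive row beside the Week 26 count. It gives the number of ITT men, among those with a baseline and at least one later on-treatment or early-withdrawal semen value, whose lowest total sperm count (Week 13, Week 26 or the early-withdrawal pair) is at least 50% below baseline. Show its denominator and the number of men lacking Week 26 data.
3. Footnote the row: the lowest of several values crosses 50% by chance more often than a single value does, and there is no control arm to calibrate this. The row therefore sits beside the Week 26 count and does not replace it.
4. Reconcile protocol 1.1.1 footnote f and 8.2.1 (early-withdrawal semen after 18 weeks) with 6.3.1 (no such limit). State in the SAP how the early-withdrawal pair is used, including a pair taken after treatment has ended.

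The cost is a few lines of SAP wording, one table row and a protocol clarification. Items 1 to 3 use samples that the protocol already provides for.

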6.1. TB Efficacy Outcomes

- Clinical outcome (incidence of bacteriologic failure or relapse or clinical failure) at 78 weeks (52 weeks after end of therapy). Participants will be classified as having a favourable, unfavourable or unassessable outcome status. Patients achieving and maintaining culture negative status without any additional treatment will be considered favourable; participants who fail on treatment (or do not complete treatment for any reason) or relapse in follow-up will be considered unfavourable. Patients completing treatment and clinically well when last seen but lost to follow-up before week 78 will be considered unassessable.
- 2. Proportion of participants with sputum culture conversion to negative status in liquid culture (MGIT) at Week 4, 8, 12, 16, 22, 26, 35, 44, 52, 65 and 78.

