## 10.4.3 Other Secondary Endpoints

#### 10.4.3.1 Efficacy (TB)

#### 10.4.3.1.1 Clinical Outcome at 78 Weeks

For the secondary endpoint of clinical outcome (bacteriologic failure or relapse or clinical failure), participants will be classified as having a favourable, unfavourable, or un-assessable outcome status which will be defined in detail in the SAP. In general, participants achieving and maintaining culture negative status without any additional treatment will be considered favourable; participants who fail on treatment or relapse in follow-up will be considered unfavourable and participants who are not assessable (and who have not already been declared as unfavourable) will be considered un-assessable and excluded from the analysis.

# 10.4.3.1.2 Culture Conversion to Negative Status at Week 4, 8, 12, 17, 22 and 26

Proportion of participants with sputum culture conversion to negative status in liquid culture (MGIT) at 4, 6, 12 and 17 weeks to be explored as a potential biomarker of outcome at 78 weeks from start of therapy.

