7.2.2. Isolated Positive Cultures

It is known that occasionally participants produce sputum samples that are "isolated positives," that is, a positive culture preceded by a series of negative cultures and followed thereafter by at least two negative cultures without an intervening positive result. This phenomenon may be the result of a sealed cavity breaking down or laboratory contamination and does not in itself signify that the participant is relapsing. In the event of a single positive culture result occurring in a participant who has previously been classified as having culture negative status (in the absence of any retreatment), the participant will not be classified as a recurrence unless a second positive culture result is obtained at a separate visit (at least 7 days apart), without an intervening negative culture or unless the participant is lost to follow up or completes the study (and is unable to be brought back) before two negative cultures are obtained. As there is a higher incidence of isolated positives with liquid culture and sometimes even serial "isolated positives", the clinical condition of the participant will also be considered in deciding whether the participant has an unfavourable outcome and re-treatment is indicated.

For example, if a participant after being culture negative has two positive cultures in a row, but is deemed to be doing well clinically, the investigator may choose to leave the participant untreated on clinical grounds. In such a case, so long as two consecutive negative cultures are eventually obtained in the absence of treatment, the participant will not be classified as an unfavourable outcome (defined in §6.1 above).

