7.2.3. Culture negative status

Culture negative status is achieved when a participant produces at least two negative culture results at different visits (at least 7 days apart) without an intervening positive culture result for MTB. The date of the first negative culture (date of collection of culture) of these two is the date at which culture negative status was obtained. Once obtained, culture negative status continues until there are two positive cultures at different visits (at least 7 days apart), without an intervening negative culture, or until there is a single positive culture not followed by two negative cultures. Culture negative status can be achieved at any time during treatment or follow-up but before any re-treatment. Culture negative status can be re-established.

Participants with two contaminated or missing samples at a given visit (from month 2 onwards) will be asked to return to produce two more sputum samples.

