8.2.1. The TB-specific modified intent-to-treat (TB-MITT) population

Defined as all participants who were enrolled and started treatment, excluding those listed below:

- 1. Any late exclusions
 - a. Participants enrolled and later found to be ineligible because of a protocol violation at enrolment (based on data collected prior to enrolment).
 - b. Participants without culture confirmation of TB at Day 1 (baseline) (or screening to week 4 if baseline is contaminated or negative)
- 2. Any participants who completed treatment and were later lost to follow-up or withdrawn from the study.
- 3. Participants who died during treatment from violent or accidental cause.
- 4. Participants who died during follow-up with no evidence of failure or relapse of TB.
- 5. Participants who are able to produce sputum at the endpoint visit, but whose endpoint visit sputum samples are all contaminated or missing, who cannot be brought back for repeat cultures, provided their last positive culture was followed by at least two negative cultures. N.B.: This does not apply to participants who are unable to produce sputum at the given endpoint, or to participants who are able to be brought back subsequently and produce negative cultures.

Participants already classified as having an unfavourable outcome will not be excluded.

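### A treatment completer lost while well after one unresolved positive culture is unassessable under SAP 6.1 but a recurrence under SAP 7.2.2

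*SAP*

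**What the plan says.** Five places bear on how a treatment completer who is later lost is classified.

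- **SAP 6.1, item 1** has an unassessable rule: "Patients completing treatment and clinically well when last seen but lost to follow-up before week 78 will be considered unassessable". The sentence before it says that participants who "relapse in follow-up will be considered unfavourable". No order of precedence between the two is given.
- **SAP 7.2.2** says a single positive in a participant with culture negative status is not a recurrence without a second positive at a separate visit, "unless the participant is lost to follow up or completes the study (and is unable to be brought back) before two negative cultures are obtained".
- **SAP 7.2.3** lets culture negative status run until two positives at different visits, "or until there is a single positive culture not followed by two negative cultures".
- **SAP 8.2.1** (TB-MITT), exclusion 2, removes "Any participants who completed treatment and were later lost to follow-up or withdrawn from the study". Exclusion 5, for contaminated or missing endpoint samples, applies only "provided their last positive culture was followed by at least two negative cultures". The section closes with "Participants already classified as having an unfavourable outcome will not be excluded", and SAP 8.2.2 repeats that sentence for TB-PP.
- **Protocol 10.4.3.1.1** says that "participants who are not assessable (and who have not already been declared as unfavourable) will be considered un-assessable and excluded from the analysis". It leaves the detailed definitions to the SAP.

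**The concern.** The unassessable rule in SAP 6.1 turns on three facts: treatment completed, clinically well at last contact, lost before Week 78. The recurrence rule in SAP 7.2.2 turns on an unresolved positive culture followed by loss. One participant can meet both, and the SAP does not say which rule applies.

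The choice affects the result in one direction. If SAP 6.1 is applied, a man whose most recent positive was never cleared leaves both the numerator and the denominator of a bacteriology-based outcome, so failure or relapse is understated. With 20 to 25 men, a single classification is visible in the reported proportion. The trial is open label (protocol 7.6), so a rule left open would be settled with the outcome in view.

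**Working it through.** **The plan's own figure.** SAP section 3 asks for 20 evaluable men and allows 20% dropout: 20 / (1 − 0.20) = 25, which matches the stated enrolment. There is no power calculation to reproduce. The main check is to apply the rules to the same participant.

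**Applying the rules.** All three men complete 26 weeks, reach culture negative status, and are clinically well when lost before Week 78.

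| Cultures before loss | SAP 7.2.2 and 7.2.3 | SAP 6.1 unassessable rule | Does an 'already unfavourable' clause settle it? |
|---|---|---|---|
| (a) Two positives at separate visits at least 7 days apart, no negative between | Recurrence, established before the loss | Met if read alone | Yes: unfavourable, retained |
| (b) One positive, not followed by two negatives | Recurrence, because he is lost; culture negative status ended | Met | Not clearly: the loss creates both classes together |
| (c) No positive left unresolved | Not a recurrence | Met | Not needed; no conflict |

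Only case (b) is in conflict. For example, a man has one positive at Week 52, feels well and cannot be traced. Before the loss he is not yet a recurrence. At the loss, SAP 7.2.2 makes him one and SAP 6.1 makes him unassessable. Exclusion 2 has no culture condition, so it removes him from TB-MITT unless he counts as already unfavourable, which is the point in dispute.

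**Contrast within SAP 8.2.1.** Exclusions 2 and 5 both deal with men who lack a usable endpoint culture. Exclusion 5 requires the last positive to have been cleared by two negatives; exclusion 2 does not.

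**Size.** Let n be the number of men otherwise in the analysis, k the number in case (b), and u the other unfavourable outcomes. Under SAP 7.2.2 the proportion is (u + k)/n; under SAP 6.1 with exclusion it is u/(n − k). The values of k and u are assumptions. Taking n = 20 (evaluable target) and n = 25 (planned enrolment), with exact (Clopper-Pearson) 95% intervals:

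| n | k | u | Scored by 7.2.2 | Scored by 6.1 and excluded |
|---|---|---|---|---|
| 20 | 1 | 0 | 1/20 = 5.0% (0.1–24.9) | 0/19 = 0% (0–17.6) |
| 20 | 1 | 1 | 2/20 = 10.0% (1.2–31.7) | 1/19 = 5.3% (0.1–26.0) |
| 20 | 2 | 0 | 2/20 = 10.0% (1.2–31.7) | 0/18 = 0% (0–18.5) |
| 25 | 1 | 0 | 1/25 = 4.0% (0.1–20.4) | 0/24 = 0% (0–14.2) |
| 25 | 2 | 0 | 2/25 = 8.0% (1.0–26.0) | 0/23 = 0% (0–14.8) |

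Each man in case (b) moves the proportion by about 4 to 5 points. The 1/20 versus 0/19 comparison means one such man plus 19 others.

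**The case against.** The strongest reply is that the documents, read together, already put unfavourable status first. SAP 6.1 has its own relapse limb. SAP 7.2.2 refers back to the unfavourable outcome in 6.1, so the two are meant to be read together, and the specific rule on a positive followed by loss would naturally govern the general rule on men lost while well. Protocol 10.4.3.1.1 and the closing sentences of SAP 8.2.1 and 8.2.2 point the same way.

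Most of this stands. A reader might infer from the SAP 6.1 sentence that any completer lost while well is dropped whatever his cultures showed, or that a confirmed relapse can leave the endpoint. The documents do not support that. In case (a) the recurrence exists before the loss. The allowance in SAP 7.2.2 for two positives left untreated on clinical grounds holds only if two consecutive negatives are eventually obtained.

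For case (b) the reply is incomplete. Three of the protective clauses depend on the word 'already', and here nothing is declared before the loss. The relapse limb of 6.1 carries no precedence, and the SAP does not state that a 7.2.2 recurrence is a 6.1 relapse. SAP 7.2.2 also notes that an isolated positive need not mean relapse and that clinical condition will be weighed. That leaves the class less certain still.

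The case is also narrow. A positive at or after Week 26 in a converted participant calls for a return visit for more sputum (protocol 1.1.1, sputum sampling), and three contact attempts precede lost-to-follow-up status (protocol 6.3.3). These steps make it less frequent but do not classify the man who still does not return. Nor does the 20% dropout allowance indicate how many there will be: men who stop before completing treatment are unfavourable under SAP 6.1, and no loss rate after completion is given.

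**Conclusion.** The concern holds for one defined participant: a treatment completer with a single positive after conversion, clinically well, lost before two negatives are obtained. SAP 6.1 and TB-MITT exclusion 2 then give a different result from SAP 7.2.2 and 7.2.3, and no clause clearly decides between them. It should not be read as a general loss of culture-positive men from the analysis, since relapse established before the loss is protected.

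The illustrated shift assumes that one or two such men occur; it could be zero. In the ITT report, if all three outcome classes are shown over 25 men, he would move between unfavourable and unassessable (1/25 = 4.0%) without disappearing from view. The outcome is among the other secondary ones in a single-arm trial analysed descriptively, and the sperm-count endpoint is not touched. A correction is still worthwhile: the rule applied literally drops a man with an uncleared positive from a bacteriological endpoint, and the SAP already contains the condition that would prevent it.

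**What to change.** Make three linked edits to the SAP before the Week 78 analysis.

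1. In 6.1, limit the unassessable class to treatment completers who are clinically well when last seen, are not unfavourable under 7.2.2, and whose last positive culture was followed by at least two negatives, with 7.2.4 applying where no sputum can be produced.
2. State in 6.1 that a recurrence under 7.2.2, including one that arises because the participant is lost, counts as unfavourable and takes precedence over unassessable.
3. Add to TB-MITT exclusion 2 the culture condition that exclusion 5 already carries. TB-PP inherits it, because 8.2.2 builds on the TB-MITT exclusions.

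The cost is a few lines of SAP text and no new data. The failure or relapse proportion may look slightly less favourable, and some isolated positives that were not true relapses will count as unfavourable, as 7.2.2 already provides.
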